### 9.4 Estimated Accrual Rate

We will enroll 24 participants over 10 months at a rate of 3 participants per month. We expect this rate to be feasible since the Wake Forest Baptist Comprehensive Cancer Center (WFBCCC) sees approximately 60 patients with colorectal cancer who initiate chemotherapy each year and thus approximately the same number will be within a year of completing treatment when the study begins (plus a potential 5 per month after that who complete treatment and become eligible). Our study team (i.e., [name], [name], and [name]) has experience working together to recruit patients diagnosed with colorectal cancer and conducting behavioral intervention research. Over 75% of patients approached have agreed to participate in our current behavioral intervention study in colorectal cancer patients initiating active treatment (K01 AT008219; PI: [name]). The proposed research is less time sensitive and intensive for participants than the current study, so we expect to have similar success.

### 9.5 Estimated Study Length

**Use of Systems Support Mapping to Guide Patient-Driven Self-Management in  
Rural and Urban Cancer Survivors**

Wake Forest Baptist Comprehensive Cancer Center (WFBCCC)  
WFBCCC # 99118

We expect the study to be completed in approximately one year (by April, 2019).

# Use of Systems Support Mapping to Guide Patient-Driven Self-Management in Rural and Urban Cancer Survivors

Wake Forest Baptist Comprehensive Cancer Center (WFBCCC)  
WFBCCC # 99118

**Appendix A – Eligibility Checklist**

IRB Protocol No. 00048866	WFBCCC Protocol No. 99118
Study Title: Use of Systems Support Mapping to Guide Patient-Driven Self-Management in Rural and Urban Cancer Survivors	
Principal Investigator: [name] [name]	

Inclusion Criteria (as outlined in study protocol)	Criteria is met	Criteria is NOT met	Source Used to Confirm * (Please document dates and lab results)
Adults ≥18 years of age			
Diagnosed with stage I-III colorectal cancer			
Within 2 years of completing active treatment for colorectal cancer			
Cognitively able to complete interviews as judged by the study team			
Able to understand, read and write English			
Exclusion Criteria (as outlined in study protocol)	Criteria NOT present	Criteria is present	Source Used to Confirm * (Please document dates and lab results)
Declined study participation			

This subject is  eligible /  ineligible for participation in this study.

OnCore Assigned PID: \_\_\_\_\_

Signature of research professional confirming eligibility: \_\_\_\_\_

Date: \_\_\_\_\_ / \_\_\_\_\_ / \_\_\_\_\_

\* Examples of source documents include clinic note, pathology report, laboratory results, etc. When listing the source, specifically state which document in the medical record was used to assess eligibility. Also include the date on the document. Example: "Pathology report, 01/01/14" or "Clinic note, 01/01/14"

**Use of Systems Support Mapping to Guide Patient-Driven Self-Management in  
Rural and Urban Cancer Survivors**

Wake Forest Baptist Comprehensive Cancer Center (WFBCCC)  
WFBCCC # 99118

**Appendix B – Reduced Review\*\* Registration Form**

**DEMOGRAPHICS**

Patient: Last Name: \_\_\_\_\_ First Name: \_\_\_\_\_

MRN: \_\_\_\_\_ ZIPCODE: \_\_\_\_\_

\*SEX:  Male  Female

\*Ethnicity (choose one):  Hispanic  Non-Hispanic

\*Race (choose all that apply):  WHITE  African American  
 ASIAN  PACIFIC ISLANDER  
 NATIVE AMERICAN (Alaskan)

\*Diagnosis: \_\_\_\_\_

DOB (mm/dd/yy): \_\_\_\_ / \_\_\_\_ / \_\_\_\_ (include if no MRN is provided)

\*MD Name (Last, First) : \_\_\_\_\_, \_\_\_\_\_

\*Date Consent Signed: \_\_\_\_ / \_\_\_\_ / \_\_\_\_

Date of Registration: (if different than consent signing) \_\_\_\_ / \_\_\_\_ / \_\_\_\_

PID # (OnCore): \_\_\_\_\_ (to be completed by registrar)

*Comprehensive Cancer Center requires that all registrations be sent to the CCCWFU Centralized Registrar the day the patient is consented; if this is not possible we require that all registration be communicated to the Centralized Registrar within 72 hours by the CRM registrar.*

*\*\*Reduced Review means eligibility and other review are not performed by CRM registrar.*

*For questions, the Protocol Registrar can be contact between 8:30 AM and 4:00 PM, Monday – Friday.*

*Completed Eligibility Checklist and Protocol Registration Form must be hand delivered, faxed or e-mailed to the registrar*

*\*\*\* if not using the full wakehealth.edu outlook client (full outlook, not web outlook) save this file and attach to an email.*

**Use of Systems Support Mapping to Guide Patient-Driven Self-Management in  
Rural and Urban Cancer Survivors**

Wake Forest Baptist Comprehensive Cancer Center (WFBCCC)  
WFBCCC # 99118

**Appendix C - Race & Ethnicity Verification Form**

*Thank you so much for helping us to verify your race and ethnicity to ensure the quality of our information. As a brief reminder, the information you provide today will be kept confidential.*

1. Are you:  
 Hispanic or Latino/a  
 Not Hispanic or Latino/a
2. What is your race? One or more categories may be selected.  
 White or Caucasian  
 Black or African American  
 American Indian or Alaskan Native  
 Asian  
 Native Hawaiian or Other Pacific Islander  
 Other, Please Specify: \_\_\_\_\_

---

---

*Internal use only:*

Name: \_\_\_\_\_ MRN#: \_\_\_\_\_

*Was the self-reported race and ethnicity of the participant verified at the time of consent?*  
 Yes  No

*Was a discrepancy found? Yes  No*

*If yes, please provide what is currently indicated in the EMR:*

Ethnicity: \_\_\_\_\_ Race: \_\_\_\_\_

Additional comments: \_\_\_\_\_

---

---

**Use of Systems Support Mapping to Guide Patient-Driven Self-Management in  
Rural and Urban Cancer Survivors**

Wake Forest Baptist Comprehensive Cancer Center (WFBCCC)  
WFBCCC # 99118

**Appendix D – Mandatory STRC SAE Reporting Guidelines**

Safety and Toxicity Review Committee (STRC; previously known as CROC) Serious Adverse Event (SAE) Notification SOP	Date: 2/2/2018
--	----------------

**Mandatory STRC SAE Reporting Requirements in WISER**

All AEs and SAEs that occur on any CCCWFU Institutional Interventional trial must be entered into the WISER system. Once these AEs and SAEs are entered, the following document describes how to initiate STRC reporting using the SAE form in WISER that is submitted for unexpected grade 4 and any grade 5 (death during protocol intervention) SAEs on CCCWFU Institutional interventional trial patients. There are multiple entities that require reporting of SAEs. Each entity has different rules for what is reported, and how it is reported.

Rules used by other entities (Institutional Review Board (IRB), AdEERS, MedWatch, etc.) should NOT be used to evaluate whether an event should be reported to STRC. Only the rules for reporting described in this document should be considered.

As defined in the NCI Data Table 4 reporting guidelines, CCCWFU Institutional Interventional studies covered by these reporting requirements are defined as: In-house, internally reviewed trials, including those collaborative studies conducted with industry sponsorship in which the center is a primary contributor to the design, implementation, and monitoring of the trial, or participation in a multi-site trial initiated by an institutional investigator at another center. Institutional trials are almost always authored by a researcher here at CCCWFU. Cooperative group protocols are not considered Institutional, but Research Base trials are classified as Institutional.

The STRC is responsible for reviewing SAEs for CCCWFU Institutional Interventional studies, as defined above. STRC currently requires that unexpected grade 4 and all grade 5 SAEs on these trials be reported to the STRC for review. All staff members assisting a PI in documenting and reporting an SAE that qualifies for STRC reporting are responsible for informing a clinical member of the STRC by phone (or in-person), followed by informing the entire committee via the required email notification.

THESE REPORTING REQUIREMENTS APPLY TO any faculty or staff member on the study team for a CCCWFU Institutional Interventional trial. Ultimately, the protocol PI has the primary responsibility for AE identification, documentation, grading and assignment of attribution to the investigational agent/intervention. However, when an SAE event as described below is observed, it is the responsibility of the person who observed the event to be sure that it is reported to the STRC.

**What is considered an SAE under this mandatory procedure?**

Any unexpected grade 4 event and all grade 5 events (death during protocol intervention) should be reported. These events should be reported if they occur while a patient is on study treatment or if they occur within 30 days of last study treatment (even if patient begins a new treatment during the 30 days). This window of 30 days should be the standard window to be used in all protocols unless a specific scientific rationale is presented to suggest that a shorter window can be used to identify events. In addition, if it is not clear whether the Grade 4 is unexpected it should be reported.

**Use of Systems Support Mapping to Guide Patient-Driven Self-Management in  
Rural and Urban Cancer Survivors**

Wake Forest Baptist Comprehensive Cancer Center (WFBCCC)  
WFBCCC # 99118

**Table 1: Summary of STRC Reporting Requirements for Institutional Pilot, Phase 1, Phase 2  
and Phase 3 Interventional Trials**

STRC reporting may not be appropriate for specific expected adverse events for protocols. In those situations the adverse events that will not require STRC reporting must be specified in the text of the

	ADVERSE EVENT					
	Grade 1, Grade 2, Grade 3		Grade 4		Grade 5	
	Unexpected	Expected	Unexpected	Expected	Unexpected	Expected
Unrelated	Not Required	Not Required	REPORT TO STRC	Not Required	REPORT TO STRC	REPORT TO STRC
Unlikely	Not Required	Not Required	REPORT TO STRC	Not Required	REPORT TO STRC	REPORT TO STRC
Possible	Not Required	Not Required	REPORT TO STRC	Not Required	REPORT TO STRC	REPORT TO STRC
Probable	Not Required	Not Required	REPORT TO STRC	Not Required	REPORT TO STRC	REPORT TO STRC
Definite	Not Required	Not Required	REPORT TO STRC	Not Required	REPORT TO STRC	REPORT TO STRC

approved protocol.

STRC notification responsibilities of the person (e.g., nurse) handling the reporting/documenting of the SAE in WISER:

1. Make a phone call (or speak in person) to the appropriate clinical member of the STRC as listed below (page if necessary)—see note 2 below
2. Enter a new SAE into the SAE module that is located in the Subject>> CRA Console in WISER WITHIN 24 HOURS of first knowledge of the event. Information can be entered and saved, but the STRC members will not be notified until a date is entered into the STRC Notification Date Field. This will ensure that all persons that need to be made aware of the event (i.e., study team members and STRC members) will be notified; remember to file a copy of your confirmation.
3. Ensure that you document that the appropriate person(s) on the STRC has been contacted. Indicate the name of the STRC clinician that was contacted in the comments field in the SAE console of the particular subject.
4. In addition, it is very important to enter whether or not the protocol should be suspended based on the discussion with the STRC clinician. This is the major function of the email notification. This should also be entered in the comments field in the SAE console of the subject.
5. Follow up/update the clinical member(s) of STRC regarding any new developments or information obtained during the course of the SAE investigation and reporting process.

Elements to complete the SAE form in the Subject Console in WISER:

1. Event Date
2. Reported Date
3. Reported by

**Use of Systems Support Mapping to Guide Patient-Driven Self-Management in  
Rural and Urban Cancer Survivors**

Wake Forest Baptist Comprehensive Cancer Center (WFBCCC)  
WFBCCC # 99118

4. If Grade 5, enter Death Date
5. Death occurred: within 30 days
6. Event Narrative: Brief description (include brief clinical history relevant to this event, including therapies believed related to event).
7. Treating Physician comments
8. PI comments if available
9. Protocol Attribution after discussion with STRC clinician
10. Outcome
11. Consent form Change Required? Y/N
12. SAE Classification \*This is required in order for the email notification to be sent\*
13. Adverse Event Details – Enter all details for each AE associated with the SAE.
  - a. Course start date
  - b. Category
  - c. AE Detail
  - d. Comments
    - i. STRC clinician name and comments
    - ii. Date of last dose before the event
    - iii. Is suspension of the protocol needed?
  - e. Grade/Severity
  - f. Unexpected Y/N
  - g. DLT Y/N
  - h. Attributions
  - i. Action
  - j. Therapy.
14. Enter Date Notified STRC -- \*This is required for the email notification to be sent\*

**Definition of Unavailable:**

As a general guideline if the first clinician that is contacted does not respond to the phone call or page within 30 minutes, then initiate contact with their backup. Allow up to 30 minutes for the backup to respond to a phone call or page before contacting another member. These times (30 minutes) are a general guideline. You must use your best judgment as a clinical research professional given the time of day, severity of the SAE, and other circumstances as to when it is appropriate to contact backup clinicians. If the event occurs near the end of day, then leave messages (voice or email) as appropriate and proceed with submitting your STRC notification form. It is important that you have taken reasonable steps and documented that you have initiated some type of contact to one or more of the clinical members of STRC.

**STRC CLINICAN RESPONSIBILITY:**

**Use of Systems Support Mapping to Guide Patient-Driven Self-Management in  
Rural and Urban Cancer Survivors**

Wake Forest Baptist Comprehensive Cancer Center (WFBCCC)  
WFBCCC # 99118

It is the responsibility of the STRC clinician to review all reported events, evaluate the events as they are reported; and communicate a response to the Investigator, event reporter and the members of STRC. The review will include but not be limited to the information reported; there may be times when additional information is needed in order for an assessment to be made and further communication directly with the investigator may be warranted. STRC reserves the right to agree with the investigator's assessment if STRC does not agree with the investigator. STRC reserves the right to suspend the trial pending further investigation. If there is any immediate danger or harm that could be present for a future patient based on the information provided in the STRC report then an immediate suspension of enrollment should be considered.

**AMENDMENTS TO PREVIOUS REPORTS**

If you are not able to supply all pertinent information with the initial submission, once the additional information is available do not submit a new report. Go to the original email that was received by STRC and others "reply to all" and entitle your email "Amendment for (list date of event and patient ID)" this will avoid duplications of the same event. List the additional information which you are reporting. This information needs to be entered into WISER as well. To do this, go to the Subject console and click SAEs on the left column. Click on the appropriate SAE number that needs updating. Then click update. This will allow you to add additional information.

**Acronyms**

STRC-Safety and Toxicity Review Committee  
SAE-Serious Adverse Event  
IRB-Institutional Review Board  
CCCWFU-Comprehensive Cancer Center Wake Forest University  
NCI-National Cancer Institute  
CPDM-Clinical Protocol and Data Management  
WISER –Wake Integrated Solution for Enterprise Research

# Use of Systems Support Mapping to Guide Patient-Driven Self-Management in Rural and Urban Cancer Survivors

Wake Forest Baptist Comprehensive Cancer Center (WFBCCC)  
WFBCCC # 99118

## Appendix E – Adverse Event Log

## WFBCCC Adverse Event (AE) Log

PI: \_\_\_\_\_

PID: \_\_\_\_\_

MRN: \_\_\_\_\_

Cycle Start Date: \_\_\_\_\_

Cycle End Date: \_\_\_\_\_

Cycle #: \_\_\_\_\_

\*Serious Adverse Event: Hospitalization; Disability; Birth Defect; Life-threatening; Death.

CTCAE Version 4 - [http://evs.nci.nih.gov/ftp1/CTCAE/CTCAE\\_4.03\\_2010-06-14\\_QuickReference\\_8.5x11.pdf](http://evs.nci.nih.gov/ftp1/CTCAE/CTCAE_4.03_2010-06-14_QuickReference_8.5x11.pdf)

Study ID: \_\_\_\_\_

Date: \_\_\_\_\_

## Appendix F – Study Questionnaires

### **Mapping to Guide Self-Management in Cancer Survivors**

#### Baseline Questionnaire

Study ID: \_\_\_\_\_  
Date: \_\_\_\_\_

Name of Facilitator: \_\_\_\_\_

Please answer each of the following questions to the best of your ability. We ask that you try not to skip any questions or write in any answers that are not given as choices for that particular question. There are no "right" or "wrong" answers for any of the questions, so please be honest in answering all questions. We encourage you not to spend too much time on any single question. Please go with your first instinct in answering most of the questions, as many of the questions ask you to state your opinion. Thank you again for your time. All responses will be kept completely confidential.

**A. The next few questions about your background are important to help describe, *in general terms*, people who are part of this study.**

A1. What is your date of birth? \_\_\_\_\_ / \_\_\_\_\_ / \_\_\_\_\_  
*Month*      *Day*      *Year*

A2. What is your current age? \_\_\_\_\_  
*Age*

A3. Are you... (check one)

- Currently married
- Currently living with partner
- Separated
- Divorced
- Widowed
- Single, never married
- Prefer not to answer

A4. What was the highest grade of school that you completed?

- Less than 8th grade
- 8th to 11th grades
- High school graduate or equivalent (GED)
- Technical or vocational school
- Some college
- College graduate
- Post-graduate degree
- Prefer not to answer

A5. How difficult is it for you (and your family) to pay your monthly bills?

- Very difficult
- Somewhat difficult
- Not very difficult
- Not at all difficult

A6. How many minutes did it take you to get to travel to the clinic? \_\_\_\_\_ minutes

A7. Do you use the internet or email, at least occasionally?

- No
- Yes

A8. How confident are you filling out medical forms by yourself?

- Extremely
- Quite a bit
- Somewhat
- A little bit
- Not at all

[figure not shown]
A9. How many times have you received income from AFDC, TANF, Work First, WIC or food stamps as an adult?

- Never
- Once
- Twice
- Three times
- Four times
- More than four times

## B. The next section will ask you some questions about your health behaviors.

**Physical activities** are activities where you move and increase your heart rate above its resting rate, whether you do it for pleasure, work or transportation. The following questions ask about the amount and intensity of physical activity you usually do. The intensity of an activity is related to the amount of energy you use to do these activities.

**Examples of physical activity intensity levels:**

Light activities • your heart beats slightly faster than normal • you can talk and sing	
Moderate activities • your heart beats faster than normal • you can talk but not sing	
Vigorous activities • your heart rate increases a lot • you can't talk or your talking is broken up by large breaths	

### B1. How physically active are you? (check one answer on each line)

	Does this accurately describe you?	
	Yes	No
a) I rarely or never do any physical activities.		
b) I do some light or moderate physical activities, but not every week.		
c) I do some light physical activity every week.		
d) I do moderate physical activities every week, but less than 30 minutes a day or 5 days a week.		
e) I do vigorous physical activities every week, but less than 20 minutes a day or 3 days a week.		
f) I do 30 minutes or more a day of moderate physical activities, 5 or more days a week.		
g) I do 20 minutes or more a day of vigorous physical activities, 3 or more days a week.		

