### 5.2.3 Health outcomes

- 5.2.3.1 Psychological stress [Perceived Stress Scale, 4-item]
- 5.2.3.2 Symptoms [PROMIS Profile 29]
- 5.2.3.3 Health behaviors [items on tobacco use, physical activity, use of CHA]

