### 9.2 Analysis of Secondary Objectives

To meet Objective 2.2.1, we will use descriptive statistics to summarize participant ratings of acceptability.

Descriptive statistics (means, standard deviations, 95% confidence intervals) will be used to summarize proximal outcomes and change in health outcomes by assessment measure to meet Objective 2.2.2. The primary interest will be in estimating the variance for use in planning future studies.

For Objective 2.2.3, the internal study team will work with external collaborators through an iterative process to facilitate a qualitative content analysis of the large quantity of textual MAP data. Specifically, we will first enter text data from the completed paper maps into a software program co-developed by [name] (external Senior Programmer, University of North Carolina-Chapel Hill Renaissance Computing Institute) and [name] (Consultant) using the *ssm* function to create a digital map. [name] will translate the text MAP data into lists that can be sorted by the study team (using the *sort* program). The *sort* program will allow us to group and code similar terms or concepts. Next, we will send our *sort* files back to [name] and he will use Python programming language to help aggregate the large amounts of textual

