**This section will ask you some questions about smoking. For the questions below, please try to select a single number.**

B2. Have you smoked at least 100 cigarettes (5 packs=100 cigarettes) in your entire life?

- Yes
- No ➔ Go to Question B6.
- Don't know / Not sure ➔ Go to Question B6.

B3. How many total years have you smoked (or did you smoke) cigarettes? Do not count any time you may have stayed off cigarettes.

\_\_\_\_\_ Years *If you smoked less than one year, write "1."*

B4. On average when you have smoked, about how many cigarettes do you (or did you) smoke a day?

A pack usually has 20 cigarettes in it.

\_\_\_\_\_ Number of cigarettes per day

B5. How long has it been since you last smoked a cigarette (even one or two puffs)?

*First check which one of the following choices applies to you. Then, if applicable, write a number on the line for how many days, weeks, months, or years it has been since your last cigarette.*

- I smoked a cigarette today (at least one puff).
- 1-7 days. ➔ Number of days since last cigarette: \_\_\_\_\_
- Less than 1 month. ➔ Number of weeks since last cigarette: \_\_\_\_\_
- Less than 1 year. ➔ Number of months since last cigarette: \_\_\_\_\_
- More than 1 year. ➔ Number of years since last cigarette: \_\_\_\_\_
- Don't know / Don't remember.

B6. Which of the following phrases best characterizes you at this time? *(Please mark only one response.)*

- Normal, no complaints, no symptoms of disease
- Able to carry on normal activity, minor symptoms of disease
- Normal activity with effort, some symptoms of disease
- Care for self, unable to carry on normal activity or to do active work
- Require occasional assistance but able to care for most of personal needs
- Require considerable assistance for personal care
- Disabled, require special care and assistance
- Severely disabled, require continuous nursing care

B7. How many times have you fallen in the last 6 months? \_\_\_\_\_ times

B8. **At any time** since you were first diagnosed with cancer, have you used any of the following complementary and alternative therapies?

	No	Yes	Have you used them in the past year?	
a. Special diets such as mostly vegetarian or low fat	0 	1 	→	0  No    1  Yes

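### Section 9.2 summarizes change in all health outcomes with means, SDs and 95% CIs, which does not fit the yes/no and category health-behavior items; physical activity has no score, and CHA change cannot be interpreted because the recall windows differ

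*Combined protocol and SAP*

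**What the plan says.** Section 5.2.3 places "Health behaviors [items on tobacco use, physical activity, use of CHA" among the health outcomes, next to perceived stress and PROMIS symptoms. Section 9.2 then gives a single rule: "Descriptive statistics (means, standard deviations, 95% confidence intervals) will be used to summarize proximal outcomes and change in health outcomes by assessment measure". It adds: "The primary interest will be in estimating the variance for use in planning future studies". That serves Objective 2.2.2, which is to describe outcome variability for later studies.

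Appendix F shows how the behaviors are recorded.

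- **Physical activity** (baseline B1, follow-up item 1): "How physically active are you? (check one answer on each line", with seven statements a to g, each answered yes or no. Line a is "I rarely or never do any physical activities". Line d is moderate "physical activities every week, but less than 30 minutes a day or 5 days a week", so it has a ceiling. Lines f and g describe activity at or above the thresholds.
- **Smoking** (baseline B2 to B5, follow-up items 2 to 5): B2 asks "Have you smoked at least 100 cigarettes (5 packs=100 cigarettes) in your entire life". B3 (years smoked) and B4 (cigarettes per day) are written-in numbers. B5 begins "First check which one of the following choices applies to you" and then takes a number in days, weeks, months or years.
- **CHA use** (baseline B8, follow-up item 8): eleven therapy groups, each yes or no.

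No activity score, no definition of current smoking, and no proportion or transition table appears in Section 9.2 for these items. Fisher's exact and Wilcoxon tests are planned there, but only to compare urban with rural participants.

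**The concern.** A mean and SD of change suit a scale score. They suit a set of yes/no lines only once someone has said what is being averaged. For physical activity nobody has, and the obvious candidates (each line separately, or the number of lines endorsed) do not rise with activity. For single yes/no items the mean of the change is usable, but the usual interval around it behaves badly when few people switch. Few switches are plausible here, with one session, follow-up at 14 to 28 days and at most 24 people.

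At stake is the stated product of Objective 2.2.2. For these behaviors the pilot could hand the next team an SD of zero, an interval that conveys more certainty than 24 people can give, or an activity gain recorded as no change. The analyst would also be choosing the activity score after seeing the data.

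**Working it through.** The plan states no figure for the health-behavior summaries, so there is none to reproduce. The power statement in Section 9.3 concerns feasibility rates only.

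**Inputs.** n = 24 (Section 2.0). About 17 would have follow-up data if retention sits at the 70% threshold in Section 2.1.1 (0.70 × 24 = 16.8). Item formats are from Appendix F. Switching rates of 2% to 20% are an assumption, because the documents give none.

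**1. Direction of the activity items.** Trace some moves through the seven lines:

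| Baseline yes | Follow-up yes | Change on line d | Change in count of yes |
|---|---|---|---|
| d | a (less active) | −1 | 0 |
| d | c (less active) | −1 | 0 |
| d | f (more active) | −1 | 0 |
| c, d | c, f (more active) | −1 | 0 (2 to 2) |
| a | b (more active) | 0 | 0 |
| d | e, f (more active) | −1 | +1 |

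Line d falls by 1 whether activity falls or rises. The count stays the same in most of these moves. This needs no assumed rate.

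**2. Yes/no items.** Let p be the chance that a person switches, in one direction. P(nobody switches) = (1 − p)^n; for example 0.98^24 = 0.616. The SD is then 0 and a t-interval runs from 0 to 0. The exact (Clopper-Pearson) upper limit for 0 of n is 1 − 0.025^(1/n), which is 14.2% for n = 24 and 19.5% for n = 17. Coverage of the nominal 95% t-interval, by enumerating the binomial:

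| p | Nobody switches, n=24 | Coverage, n=24 | Nobody switches, n=17 | Coverage, n=17 |
|---|---|---|---|---|
| 2% | 62% | 38% | 71% | 29% |
| 5% | 29% | 71% | 42% | 58% |
| 10% | 8% | 92% | 17% | 83% |
| 20% | 0.5% | 95% | 2% | 87% |

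With 1 switch in 24, the mean is 1/24 = 4.2%, the SD is 0.204, and the t-interval is −4.5% to 12.8%. The exact interval is 0.1% to 21.1%. With 5 in 24, the intervals are 3.3% to 38.4% and 7.1% to 42.2%, equal in width. If switching runs both ways (5% start, 5% stop), the t-interval at n = 24 covers 98% and has zero width with probability 8%. The shortfall therefore belongs to rare, mainly one-way change.

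**3. Smoking.** B3 and B4 are numbers, so a mean and SD can be computed. B5 is a category plus a number in one of four units, with no conversion rule and no cut-point for current smoking.

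**4. CHA windows.** Baseline B8 asks about any use since diagnosis and then about the past year. Follow-up item 8 asks about the past 2 weeks. The past-year window is 52/2 = 26 times as long. A person who used a therapy some months ago and changed nothing moves from yes to no. Since yes-to-no moves do not mean stopping, no before-after difference on these items measures change, whatever statistic or interval is put on it.

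**The case against.** Section 9.2 names no interval formula. The mean of a 0/1 item is a proportion, and an exact interval would also satisfy the wording. The planned Fisher and Wilcoxon tests show that the team expects categorical data. Nothing in the plan says that activity lines will be counted or averaged, and a highest-level score would rise with activity. These are descriptive secondary items in a feasibility pilot, with no test of change.

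Most of this stands as a limit on the claim. It does not remove the gap: the rule names means and SDs, the categorical methods are confined to the rural-urban comparison, and a sensible activity score is possible but not specified.

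A reader might infer more than the documents support:

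- That the method always gives zero-width or falsely tight intervals. It does so only if a t-type interval is used and switching is rare. At n = 24 and 20% switching, coverage is 95%.
- That all the smoking items are boxes. B3 and B4 are numeric.
- That activity change has no direction under any scoring. That holds for item or count scoring only.
- That a narrow interval for mean smoking change over all participants is shown to be wrong by a wide interval for quitting among the few smokers. Those are two different quantities.
- That the next trial will be mis-sized. No section says that a health behavior will be the outcome used to size it.

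**Conclusion.** The point holds in a limited form. The single summary rule in Section 9.2 does not fit the yes/no and category items that Section 5.2.3 includes among the health outcomes.

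Two parts rest on the forms alone: no physical-activity score is specified, and CHA change cannot be interpreted with the present windows. The interval part is conditional. It assumes a t-interval, rare one-way switching and 17 to 24 people with data. On those terms the chance of an interval of zero width at n = 24 runs from 62% at 2% switching down to 0.5% at 20%.

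Feasibility, the primary objective, is untouched. The plan should still be corrected, because variability is what these summaries are for and the correction is cheap.

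**What to change.** In Section 9.2:

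- Keep means, SDs and 95% CIs for scale scores and for numeric items such as B3 and B4.
- Score physical activity at each visit as one ordered level, the highest of lines a to g endorsed, plus a yes/no for line f or g. Show the baseline-by-follow-up table.
- Define current smoking from B5 with the same cut-point at both visits, and state how people routed past B5 by their B2 answer are classified. Report n/N at each visit and the paired transition counts, with exact binomial 95% CIs.
- For CHA, choose one of two routes. Either add a past-2-weeks question to baseline B8, so that paired counts mean something, or report each visit separately as n/N with exact CIs and make no claim about change. Started and stopped counts on the present forms would mislead.

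The cost is a few sentences in Section 9.2 and some cross-tabulations. Aligning CHA adds one column to the baseline form and helps only participants not yet assessed at baseline; the by-visit route needs no new data. The exact intervals will be wider when few people switch, which reflects what the sample can support.
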